Exploratory Aim: To examine whether symptom severity, social anxiety, mood, attachment style, and rejection sensitivity moderate the effects of oxytocin.

III. Subject Selection

Inclusion Criteria for BDD Groups:

1. Treatment-seeking adult males and females \geq 18 years of age
2. Meets DSM-IV criteria for principal BDD as determined by Structured Clinical Interview for DSM-IV (SCID) diagnostic interview
3. For females only: must be using low-dose hormonal contraceptives, as defined by <50 mcg daily dose of ethinyl estradiol. Female participants will bring medication labeling to the screening visit so study staff may verify acceptable drug composition.

Exclusion Criteria for BDD Groups:

1. Current diagnosis of schizophrenia, psychotic disorder, bipolar disorder, substance abuse or substance dependence. All other Axis I comorbidities will be permitted to foster the accrual of a clinically relevant sample.
2. Significant nasal pathology (e.g., atrophic rhinitis, history of hypophysectomy, recurrent nosebleeds)
3. Smokers who smoke \geq 15 cigarettes daily
4. Serious medical illnesses (including untreated thyroid disease, diabetes, cardiovascular disease, and seizures, as assessed by medical history). Individuals who are taking levothyroxine or who report a history of thyroid disease will be given a blood test to determine thyroid hormone levels and eligibility for the study.
5. Active homicidal or suicidal ideation
6. Steroid or hormone use (except low-dose contraceptives for females, which is allowed)
7. For females only: positive urine pregnancy test and use of high dose contraceptives (low dose contraceptives will be allowed due to stability of hormone levels during active phase)

Inclusion Criteria for Control Participants:

1. Adult males and females \geq 18 years of age
2. No current DSM-IV Axis I diagnosis, as determined by SCID
3. For females only: must be using low-dose hormonal contraceptives, as defined by <50 mcg daily dose of ethinyl estradiol. Female participants will bring medication labeling to the screening visit so study staff may verify acceptable drug composition.

Exclusion Criteria for Control Participants:

1. Current diagnosis of any DSM-IV Axis I disorder
2. Significant nasal pathology (e.g., atrophic rhinitis, history of hypophysectomy, recurrent nosebleeds)

3. Smokers who smoke \geq 15 cigarettes daily

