intranasal administration of oxytocin (MacDonald et al., 2011). The nasal sprays (Syntocinon® nasal spray, 40 IU/ml) will be purchased from Pharmaworld and manufactured by Novartis in Switzerland under an Investigational New Drug (IND) application from the Food and Drug Administration. The principal investigator, [name]., and study physician, [name]., both have experience obtaining an IND for intranasal oxytocin, and are familiar with the sponsor-investigator responsibilities associated with maintaining the IND. As the physician on the IND, [name] will provide medical oversight regarding reported adverse events, as well as risk coverage for subjects enrolled in the study. Subjects will follow a standardized protocol for self-administering the metered dose nasal sprays (see attached administration protocol) with three sprays per nostril (4 IU oxytocin per spray). A study nurse at the MGH Clinical Research Center, who will be blind to the subject's assigned drug condition, will be present for drug administration. Only the MGH Research Pharmacy will be un-blinded to drug condition during the study, as they will be responsible for treatment assignment at each study visit.

Clinician-Administered Measures:

Structured Clinical Interview for DSM-IV-TR (SCID; First, Spitzer, Gibbon, & Williams, 2002): The SCID is a clinician-administered, semi-structured interview that assesses current Axis I disorders. Given that the SCID has not yet been updated to reflect DSM-5 diagnostic criteria, we will assess diagnoses based on DSM-IV criteria. The SCID will be administered during the screening visit to diagnose participants, characterize the sample, and screen for other eligibility criteria.

Demographics and Eligibility Form: This clinician-administered measure will be developed specifically for the purposes of this study to assess demographic information, and to document other inclusion and exclusion criteria (e.g., medical illnesses, nasal pathology, suicidal/homicidal ideation, cigarette use, concurrent medications, steroid use, pregnancy test results).

Yale-Brown Obsessive-Compulsive Scale modified for BDD (BDD-YBOCS; Phillips, Hollander, Rasmussen, & Aronowitz, 1997): The BDD-YBOCS is a 12-item clinician-administered severity rating scale for BDD. It will be administered during the screening visit. (BDD participants only)

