Brown Assessment of Beliefs Scale (BABS; Eisen et al., 1998): The BABS is a 7-item clinician-administered scale to assess degree of insight and conviction of beliefs. It will be administered during the screening visit to assess degree of delusionality. (BDD participants only)

Self-Report Questionnaires:

Body Dysmorphic Disorder Symptom Scale (BDD-SS; Wilhelm, unpublished): The BDD-SS revised is a self-report measure that assesses severity of specific BDD symptom domains. The scale organizes symptoms into conceptually similar clusters, such as checking and comparing, fixing and correcting, weight and shape concerns, skin picking

and hair pulling, avoiding and hiding, seeking cosmetic surgery, and beliefs about appearance.

Liebowitz Social Anxiety Scale- Self-Report (LSAS; Liebowitz, 1987): The LSAS is a 24-item measure that assesses fear and avoidance of social situations in the past week. It is widely used in treatment studies for SAD. The LSAS has been validated in clinical samples and has high internal consistency ($\alpha = .82\text{-.92}$) (Heimberg et al., 1999).

Brief Fear of Negative Evaluation Scale (BFNE; Leary, 1983): The BFNE is an abbreviated 12-item self-report questionnaire adapted from the original Fear of Negative Evaluation Scale (Watson & Friend, 1969), which measures apprehension about others' evaluations, expectation for negative evaluation, avoidance of evaluative situations, and distress associated with negative evaluation.

Interpersonal Sensitivity Measure (IPSM; Boyce & Parker, 1989): The original IPSM is a 36-item self-report measure to assess sensitivity to rejection. It has been demonstrated to have good internal consistency (Boyce & Parker, 1989; Harb, Heimberg, Fresco, Schneier, & Liebowitz, 2002).

Experience in Close Relationships Inventory (ECR; Brennan et al., 1998): The ECR is a 36-item self-report questionnaire that measures attachment anxiety and avoidance in adults. It yields two subscales reflecting attachment anxiety (anxiety about being rejected or abandoned) and attachment avoidance (discomfort with closeness and intimacy).

Depression Anxiety Stress Scale-21 (DASS; Lovibond & Lovibond, 1995): The DASS is a shortened, 21-item version of the original DASS self-report questionnaire designed to measure dimensional aspects of depression, anxiety, and stress.

Positive and Negative Affect Scales (PANAS; Watson, Clark, & Tellegen, 1988): The PANAS is a 20-item self-report measure of positive and negative affect.

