Prior to analysis, all major variables will be screened for inconsistent or abnormal values, and continuous measures assessed for skewness and outliers. Variable distributions will be examined and transformations made when distributions are skewed or otherwise violate analytic assumptions. Linear regression models will be used, and in all models, the effect of diagnosis will be based not on the global (type III) effect, but on the specific pair-wise comparison of interest: BDD vs. Healthy Controls. Analyses will be conducted using SAS v9.4 (SAS Institute, Cary, NC), and all models will employ a two-sided alpha=0.05 to determine significance.

Aim 1 Analyses:

The primary outcomes will be the Emotion Recognition Task total score and the Trust Game "back transfer" amount. Two sets of outcome scores will be obtained for each subject - one during placebo and the other during oxytocin administration. To test Hypothesis 1a, we will regress placebo outcome scores against diagnosis. To test Hypothesis 1b, we will regress oxytocin outcome scores against diagnosis, and will control for the placebo outcome score. If we find significant differences in oxytocin Emotion Recognition Task total score by diagnosis, we will further examine the 3 Emotion Recognition Task valence categories (positive, negative, neutral) as exploratory outcomes.

Aim 2 Analyses:

Secondary outcomes include the Posner Task difference score for disengagement response latencies between disgust vs. neutral faces, and the Interpretation Questionnaire total score. Mirroring the analyses for the primary aim, we will test Hypothesis 2a by regressing the placebo secondary outcome scores against diagnosis, and will test Hypothesis 2b by regressing the oxytocin secondary outcome scores against diagnosis, controlling for the placebo secondary outcome scores.

Exploratory Analyses:

Exploratory moderators include the BDD-YBOCS total score, YBOCS total score, LSAS total score, BFNE total score, ECR Anxiety subscale mean, ECR Avoidance subscale mean, and IPSM total score. To test the moderation effects, we will enter each moderator (one at a time) into each of the aforementioned linear regression models along with a covariate representing the interaction between the moderator and diagnosis (the term of interest). We will examine moderation of each pair-wise comparison separately.

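### The exploratory moderator analysis has no mood score, tests only whether moderation differs by diagnosis, and lists two scores that cannot be tested as written

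*Combined protocol and SAP*

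**What the plan says.** Section II states the Exploratory Aim: "To examine whether symptom severity, social anxiety, mood, attachment style, and rejection sensitivity moderate the effects of oxytocin". That is five constructs, and the thing moderated is the effect of oxytocin.

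Section VI, Exploratory Analyses, gives the scores: "Exploratory moderators include the BDD-YBOCS total score, YBOCS total score, LSAS total score, BFNE total score", followed by "ECR Anxiety subscale mean, ECR Avoidance subscale mean, and IPSM total score". That is seven scores. Each is to be added singly to every regression already described, together with "a covariate representing the interaction between the moderator and diagnosis (the term of interest"). Those regressions are the placebo score on diagnosis (Hypotheses 1a and 2a) and the oxytocin score on diagnosis with the placebo score as covariate (1b and 2b). The paragraph ends by saying that moderation will be looked at for each pairwise group comparison.

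Section V describes the instruments. The DASS-21 is a "self-report questionnaire designed to measure dimensional aspects of depression, anxiety, and stress". The next entry reads "The PANAS is a 20-item self-report measure of positive and negative affect". Neither is restricted to one group, and the study overview places the self-report questionnaires at the first visit, before any spray. For the Yale-Brown family, section V has only this: "The BDD-YBOCS is a 12-item clinician-administered severity rating scale for BDD". It is given at screening, to BDD participants only. No plain YBOCS is described.

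**The concern.** The aim and the analysis do not line up in three places.

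- Mood is a named construct with no named score. The choice among several DASS-21 and PANAS scores would have to be made later, possibly after the data are seen.
- The designated term compares moderation between the two groups. The aim, as worded, asks whether moderation exists. A factor that acts alike in both groups is invisible to that term.
- Two listed scores cannot be run as specified: one exists in only one group, and the other has no described assessment.

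At stake is whether the Exploratory Aim gets an answer from data the study already collects. Nothing confirmatory depends on it.

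**Working it through.** **Plan's own figure.** The plan gives no power or precision for the moderator analyses. Its one design figure is 81% power at f = 0.23 for the primary comparison. A within-between interaction F test with N = 40, two measurements and an assumed placebo-oxytocin correlation of 0.5 has noncentrality 0.23² × 40 × 2 / (1 − 0.5) = 8.464 on 1 and 38 df, and power 80.9%. The figure is reproduced under that assumption. It does not bear on this point.

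**Coverage of the aim.**
- Symptom severity: BDD-YBOCS (and YBOCS).
- Social anxiety: LSAS, BFNE.
- Attachment style: the two ECR subscales.
- Rejection sensitivity: IPSM.
- Mood: none.

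Four of the five constructs are covered.

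**What the test term measures.** With diagnosis coded 1 for BDD and 0 for controls, and leaving out the medication covariate, the 1b/2b model becomes

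oxytocin = b0 + b1·diagnosis + b2·placebo + b3·moderator + b4·moderator×diagnosis.

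The moderator's slope on the placebo-adjusted oxytocin score is b3 in controls and b3 + b4 in BDD. The term of interest is b4, the difference between the slopes. If the slope is 0.5 in both groups, b3 = 0.5 and b4 = 0. In the 1a/2a models the outcome is the placebo score, so no oxytocin data enter at all.

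**Simulation.** Assumptions: 20 per group, standardised moderator independent of the placebo score, placebo-oxytocin correlation 0.5, residual SD √0.75, a medication covariate at 30%, 3,000 runs, two-sided 0.05. The last column is the moderator coefficient in the same model without the interaction.

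| True slopes (BDD, controls) | Moderator × diagnosis | Common moderator slope |
|---|---|---|
| 0, 0 | 4.5% | 5.4% |
| 0.3, 0.3 | 4.8% | 51.8% |
| 0.5, 0.5 | 4.8% | 90.7% |
| 0.8, 0.8 | 5.1% | 99.8% |
| 0.5, 0 | 37.7% | 35.9% |
| 0.5, −0.5 | 87.4% | 7.2% |

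Shifting the BDD moderator mean by 2 SD, with slopes of 0.5 in both groups, gives 5.0% and 89.9%. The last two rows show why the interaction should be kept: the two quantities answer different questions.

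**BDD-YBOCS.** With values in BDD only, the intercept and diagnosis columns are identical, and so are the moderator and interaction columns. The five-column design has rank 3. Coding controls as zero would not help, because the moderator and interaction columns would still coincide. Within BDD, a single slope can be estimated.

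**Count.** Seven scores × four outcomes = 28 planned tests in the oxytocin models. Removing the BDD-YBOCS and YBOCS leaves 5 × 4 = 20 that can be run as written.

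**Choice of metric.** The slope on the oxytocin-minus-placebo difference is the moderator coefficient plus (b2 − 1) × g, where g is the slope of the placebo score on the moderator. The two agree only if b2 = 1 or g = 0. With assumed b2 = 0.5 and g = 0.5, they differ by (0.5 − 1) × 0.5 = −0.25. One metric must therefore be fixed in advance.

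**The case against.** The strongest defence is that moderator × diagnosis is the right term. Aim 1 concerns effects that differ by diagnosis, Hypotheses 1b and 2b compare BDD with controls, and the exploratory paragraph says that the pairwise comparison is what is being moderated. This stands: in the 1b and 2b models the term properly asks whether a factor changes the BDD-control difference. A reader might infer that the plan uses a wrong test; the documents do not support that. What remains is that the aim in section II is worded more broadly than the term can answer.

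A reader might also infer that a moderator shared by both groups would be reported as no moderation. The plan sets no such reporting rule, and b3 is in the planned model and would be estimated. The 5% figure follows from assuming equal slopes. It shows what the term cannot see and does not forecast the report.

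The YBOCS entry, taken alone, is editorial: a score without data biases nothing. The mention of three study groups in the recruitment section, and an uncited YBOCS reference, suggest residue from a dropped group, but that is inference.

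Finally, the list is introduced with an open-ended verb, so a mood score is not excluded. None is named anywhere in section VI, however, so the gap stands.

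**Conclusion.** The point holds as a consistency and completeness defect in an exploratory analysis. One of five constructs has no named score. Two of seven listed scores cannot be tested as written. The designated term answers a narrower question than the stated aim, and in the placebo-only models it does not concern oxytocin.

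The coverage, algebra and rank results need no outside figures. The detection rates rest on the assumed correlation, medication rate and slopes; the roughly 5% rate under equal slopes does not depend on the size of the slope. The primary and secondary analyses and the stated 81% power are untouched. The change is worth making because the data are already being collected.

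**What to change.** In section VI, Exploratory Analyses:

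1. Name at least one collected mood score as a moderator, for example DASS-21 Depression, or PANAS Positive and Negative Affect.
2. In the 1b and 2b models, report each moderator's slope on the placebo-adjusted oxytocin score within BDD (b3 + b4) and within controls (b3), with confidence intervals, as the answer to the Exploratory Aim. Use that metric throughout, and state that it can differ from a slope on the oxytocin-minus-placebo difference when the moderator is related to the placebo score.
3. Keep moderator × diagnosis as the separate test of whether the slopes differ. Do not present its use in the 1a and 2a models as evidence on oxytocin.
4. Analyse the BDD-YBOCS within BDD only.
5. Delete the YBOCS entry unless the scale is added to the measures.

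The cost is wording, plus more exploratory estimates. With one mood score there are six two-group moderators × three quantities × four outcomes = 72, plus 4 for the BDD-YBOCS, so 76. With three mood scores the total is 8 × 3 × 4 + 4 = 100. Each within-group slope rests on about 20 people. Under the simulation's assumptions its standard error is roughly 0.866/√20 = 0.19, a 95% interval of about ±0.38 before allowing for lost degrees of freedom. Label the results exploratory and not adjusted for multiplicity.

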An advanced doctoral student or a doctoral level member of the study staff will obtain written informed consent, and will thoroughly review the consent form with the potential participant. If an advanced doctoral student obtains consent, a licensed physician investigator will be available to speak with the subject during the consent process. Subjects who are consented by advanced doctoral students will be offered the option of speaking with a physician Investigator during the consent process and this will be recorded in research records. During the consenting process, potential participants will be apprised of the voluntary nature of their participation in the study and that they can withdraw at any point in the study without penalty. Specifically, we will reassure all potential participants that refusal to participate will in no way influence their care or affiliation with the Clinics at the Massachusetts General Hospital or any other Harvard Medical School affiliated hospital. Potential participants will be informed that the study will examine how oxytocin impacts their performance on different social cognitive tasks, but they will not be informed as to the exact study hypotheses (e.g., how oxytocin's effects on social and cognitive functioning may relate to their BDD symptoms). It will be necessary to use incomplete disclosure at the outset of the study to ensure maximum internal validity of study results. Potential participants will also be given as much time as needed to consider participation, and will be given an opportunity to ask questions about the study prior to signing the consent form. We will obtain written informed signed consent through the use of a PHRC approved written consent from all participants before they enter into the study and start study procedures. After signing the consent form, participants will be given a copy of the consent, and the original copy will be filed in a locked file separate from study data in a research office.

[figure not shown]
Treatment Assignment Procedures:

Given the cross-over design, all participants will receive an oxytocin and placebo nasal spray at two separate visits. The MGH Research Pharmacy will randomize the order of nasal sprays that will be given to participants, and will thus be un-blinded of assigned drug condition for participants' study visits. All other study staff, as well as participants themselves, will be blind to drug condition.

V. Study Procedures

Overview of Study Procedure:

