For all analyses, we will include concomitant medication use as a covariate, in order to control for the effect of concomitant medications on study results. We will also compare participants who are taking psychotropic medications from participants who are not, on

demographic and clinical variables, to ensure there are no systematic differences between these groups.

Power and Sample Size:

Given the novelty of our approach, no background data on the effects of oxytocin in BDD exist to inform the power calculation. Therefore, the proposed sample size of 40 participants (20 per group) was chosen based on feasibility. With 20 participants per group and a two-sided alpha=0.05, for our primary pair-wise comparison (BDD vs. healthy controls) of the mean within-subject difference (oxytocin vs. placebo) in Emotion Recognition Task total score and Trust Game "back transfer" amount, we will have 81% power to detect a moderate effect size of $f=0.23$.

VII. Risks and Discomforts

Oxytocin-Related Risks and Side Effects:

Between 1990 and 2010, there have been 38 controlled studies involving intranasal delivery of oxytocin (MacDonald et al., 2011). A total of 1,529 participants have received intranasal oxytocin or placebo, and nine studies have included participants (N=182) who had a developmental, medical, or mental health disorder. The dosage of oxytocin has typically been a single dose ranging from 20 international units (IU) to 40 IU. Out of the 1,529 participants who have received intranasal oxytocin or placebo, 279 (18%) reported mild side-effects (MacDonald et al., 2011). The most common side-effect was a feeling of calmness, but this did not differ between those who received oxytocin or placebo. A recent review of studies using intranasal oxytocin supported the short-term use of oxytocin, demonstrating that oxytocin produced minimal side-effects, no detectable differences in side-effects between oxytocin or placebo recipients, no subjective changes in recipients, and is equally safe to use with vulnerable populations as with healthy adults (MacDonald et al., 2011). The proposed study intends to use a single 24 IU dose of intranasal oxytocin, which has been the most commonly used dose in previous trials (25 out of 38 studies).

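### The BDD-YBOCS × diagnosis interaction, named as the term of interest, cannot be estimated because only BDD participants receive the scale; a within-BDD slope can be, but the plan does not name it as the test

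*Combined protocol and SAP*

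**What the plan says.** The Exploratory Aim (section II) is "To examine whether symptom severity, social anxiety, mood, attachment style, and rejection sensitivity moderate the effects of oxytocin". Section VI, Exploratory Analyses, begins its list of moderators: "Exploratory moderators include the BDD-YBOCS total score, YBOCS total score, LSAS total score, BFNE total score"; the two ECR subscales and the IPSM follow, making seven. Each is entered one at a time into every earlier regression, "along with a covariate representing the interaction between the moderator and diagnosis (the term of interest"). The opening of section VI defines the diagnosis effect as BDD versus healthy controls.

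The earlier regressions are of two kinds for each of four outcomes. For Hypothesis 1a, "we will regress placebo outcome scores against diagnosis"; 2a mirrors it. For 1b and 2b, the oxytocin score is regressed on diagnosis with the placebo score as a covariate. In addition, "For all analyses, we will include concomitant medication use as a covariate".

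Section V, Clinician-Administered Measures, says of the BDD-YBOCS: "It will be administered during the screening visit. (BDD participants only"). Nothing in the document gives controls a score, sets a rule for filling one in, or exempts this scale from the interaction model.

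**The concern.** An interaction with diagnosis compares the moderator's slope in BDD with its slope in controls. With no BDD-YBOCS scores in controls there is no second slope, so the quantity the plan singles out does not exist in the data. More participants would not help.

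Symptom severity comes first in the Exploratory Aim, and the BDD-YBOCS is the only BDD-specific severity score among the listed moderators. An analyst following the text will meet a dropped or aliased term and will have to choose a substitute, possibly with the data in hand. A coefficient printed beside the interaction label could also be read as a BDD-control difference when it is only a slope within BDD.

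**Working it through.** The plan gives no figure for this analysis. Its one design figure, 81% power at f=0.23 for the primary comparison, reproduces as 80.9% with λ = 0.23² × 40 × 2 / (1 − 0.5) = 8.46 on 1 and 38 df. The within-subject correlation of 0.5 is assumed. That figure has no bearing on what follows.

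**Inputs.** From the document: 20 BDD and 20 controls; D = 1 for BDD and 0 for controls; M = BDD-YBOCS, observed only when D = 1; two-sided alpha 0.05. Assumed: medication use is one yes/no column.

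**Columns.** The 1b/2b models have 6: intercept, D, placebo score, medication, M, M×D. The 1a/2a models have 5, lacking the placebo score.

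**Complete cases.** All controls drop out. Then D equals the intercept and M×D equals M, which are two exact redundancies. Rank is 6 − 2 = 4 of 6 and 5 − 2 = 3 of 5.

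**Controls filled with a constant c.** M = M×D + c − c×D holds exactly, which is one redundancy. Rank is 5 of 6 and 4 of 5, confirmed numerically for several values of c. The interaction coefficient is not estimable in either case. For a scale that varies in both groups, rank is 6 of 6 and 5 of 5.

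**Count.** (2 primary + 2 secondary outcomes) × 2 models = 8, of which 4 are 1b/2b and 4 are 1a/2a. Over seven moderators the literal total is 56. The three conditional valence outcomes would raise 8 to 11.

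**What survives.** Once redundant columns are dropped, complete cases leave exactly the within-BDD slope. A constant fill leaves a BDD slope fitted with placebo and medication coefficients shared with controls.

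**Which within-BDD model.** Suppose oxytocin does nothing. Write each score as true performance plus error: P = T + e₁ under placebo, O = T + e₂ under oxytocin. P is an imperfect proxy for T, so if severity is correlated with T it still predicts O after adjustment for P. The difference O − P = e₂ − e₁ is unrelated to severity. Simulation with n=20 and no oxytocin effect in anyone (reliability and correlation assumed; the document gives neither):

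| Task reliability | Severity-performance correlation | Rejection, placebo-adjusted slope |
|---|---|---|
| 0.7 | 0.5 | 11.7% |
| 0.5 | 0.5 | 13.9% |
| 0.5 to 0.8 | 0.3 to 0.6 | about 6% to 20% |

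The difference-score slope rejected about 5% of the time throughout.

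**Power of the difference-score slope.** Three parameters leave 20 − 3 = 17 df. At a partial correlation r = 0.30, f² = 0.09/0.91 = 0.099 and λ = 20 × 0.099 = 1.98; the noncentral F gives 26%, or 24% when λ is averaged over chi-square(18) for random predictors. Power of 80% needs r of about 0.55 (fixed) to 0.59 (random). The placebo-adjusted form (16 df) is similar: 26% and 23% at r = 0.30, and 80% at 0.555 to 0.606.

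**The case against.** The strongest reply is that little is lost. A reader might infer that the plan yields no BDD-YBOCS result, or that the severity part of the Exploratory Aim cannot be met. Neither follows. The plan also enters the moderator itself, and its slope within BDD is estimable once the redundant columns go. The aim asks whether severity moderates the effects of oxytocin, which can be studied within BDD. This part of the reply stands: the gap lies in the named test and its interpretation.

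Second, eight is a literal count. The 1a/2a models use placebo scores only, so if the aim governs the wording, only the four 1b/2b models count. This also stands, and is why the two sets are reported separately.

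Third, the problem would show at the first model run. Probably so, but the replacement would then be chosen after the data were seen.

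Fourth, the self-report BDD-SS carries no BDD-only restriction and could keep an interaction with diagnosis. That would need controls to complete it with scores that vary, which the document does not establish, and it is not on the moderator list.

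It is also tempting to conclude that the whole moderator list is unworkable. The LSAS, BFNE, ECR and IPSM carry no such restriction, and their interactions are estimable in rank terms. The YBOCS has a different gap: it is listed as a moderator but has no entry among the measures. The mention of three study groups in the recruitment section, and "We will examine moderation of each pair-wise comparison separately", suggest text left from a three-group design. That is an inference only.

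**Conclusion.** The concern holds for the BDD-YBOCS × diagnosis term: it is not estimable in any model it enters, namely four 1b/2b models and, on a literal reading, four 1a/2a models. This follows from the algebra and rests only on controls having no BDD-YBOCS scores or sharing one constant value. The choice of replacement model rests on assumed task reliability and an assumed severity-performance correlation, so the 6% to 20% range illustrates a risk and does not estimate it for this trial.

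Severity is minor. The analyses are exploratory and no primary or secondary test changes. A reader might infer from "All other study staff, as well as participants themselves, will be blind to drug condition" that the change can certainly precede unblinding. That sentence says who is blinded, not where the trial stands, and the adverse-event section already refers to participants in the study to date.

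**What to change.** For the BDD-YBOCS only, replace the interaction with:

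> In BDD participants, regress the oxytocin-minus-placebo difference on BDD-YBOCS and medication use; the term of interest is the BDD-YBOCS slope; hypothesis-generating, n=20.

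If the placebo-adjusted form is kept, state that its slope can reflect an association between severity and task performance when the task is imperfectly reliable. Do not present 1a/2a models containing the BDD-YBOCS as moderation of oxytocin.

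A BDD slope fitted on all 40 participants is not recommended. At a partial correlation of 0.50 its simulated power was 64% against 59% for the placebo-adjusted slope within BDD, and its type I error reached 11.7% when the control residual SD was assumed to be half that in BDD.

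Clean-up: delete the YBOCS from the moderator list unless it is in fact collected.

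The cost is SAP wording, with no new visit, measure or participant. This moderator will no longer offer a BDD-control comparison, and power stays low. Make the change before unblinding if that is still possible; otherwise record when it was made and label the analysis accordingly.
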